11.6.3. Growth Data

Triplicate stadiometric height measurements, as well as the average of each set of triplicate measurements, will be collected at each planned visit according to the Protocol Defined Schedule of Events (see Section 11.2.1). The average will serve as the participant’s height at that clinic visit.

Growth Data
Growth Velocity Calculation

 • Growth velocity will be calculated for each participant over each study period (i.e., baseline, double-blind treatment, and follow-up) by fitting a regression line to the height measurements recorded for that participant during the period. The slope of this regression line will be the participant’s growth velocity for that study period. • Stadiometric height measurements obtained at Visits 1, 3, and 5 will be used to determine the baseline period growth velocity, which will be calculated based on data from at least two of these visits. • Stadiometric height measurements obtained at Baseline (Visit 5) and during the double-blind treatment period (Visit 6 up to and including Visit 18) will be used to determine the double-blind treatment period growth velocity. Separate estimands for growth velocity during the double-blind treatment period will be considered in the Growth and ITT populations (as defined in Section 7.1: Primary Growth Analyses). • Stadiometric height measurements obtained at Visits 18 and during the follow-up period will be used to determine the follow-up period growth velocity. • Stadiometry measurements obtained during the Early Withdrawal/Early Treatment Discontinuation Visit will be included in the calculation of the growth velocity over the double-blind treatment period.
Growth Velocity Below the 3rd Percentile

 • Using Table VIIA and Table VIIB in Standards from Birth to Maturity for Height, Weight, Height Velocity, and Weight Velocity: British Children, 1965 Part II (Tanner, 1966) data values for the 3rd percentile for growth velocity will be input into an Excel spreadsheet and then imported into the SAS programming environment. • Each participant’s double-blind treatment period growth velocity, calculated based on all on- and off-treatment height data, will be programmatically compared to these imported data using the 3rd percentile value of the age closest to the participant’s age at the end of the endpoint (i.e., either the end of the participant’s double-blind treatment period [Visit 18] or withdrawal from study [Early Withdrawal Visit]).
Change from Baseline in Growth Velocity Quartiles

 • Growth velocity quartile (defined as 1Q = 1st – 25th percentile, 2Q = 26th – 50th percentile, 3Q = 51st – 75th percentile, 4Q = 76th – 100th percentile) will be determined for each participant at both baseline and endpoint. • Baseline growth velocity will be calculated as the slope from a simple linear regression of the average stadiometric height measurements recorded at Visits 1, 3, and 5. • Endpoint growth velocity will be defined as the slope of a simple linear regression of the average stadiometric height measurements recorded at Visit 12 up to and including Visit 18 and will include both on- and off-treatment measurements. • Using Table I in Special Article: Clinical longitudinal standards for height and height velocity for North American children (Tanner, 1985) and Table VIIA and Table VIIB in Standards from Birth to Maturity for Height, Weight, Height Velocity, and Weight Velocity: British Children, 1965 Part II (Tanner, 1966), data values for the 25th, 50th, and 75th growth velocity percentiles will be input into an Excel spreadsheet and then imported into the SAS programming environment.

- Each participant’s baseline period growth velocity will be programmatically compared to these imported data using the participant’s estimated age at Visit 5 and age in the imported data that is closest to the actual age of the participant to determine the participant’s baseline growth velocity quartile.
- Each participant’s endpoint growth velocity will be programmatically compared to the imported data using the participant’s age at endpoint (age at the last Visit included in the endpoint) and age in the imported data that is closest to the actual age of the participant to determine the participant’s endpoint growth velocity quartile.
- Shifts from baseline will be determined as follows:

Analysis category	Change from baseline
Increase	1Q to 2Q, 3Q or 4Q; 2Q to 3Q or 4Q; 3Q to 4Q
Decrease	4Q to 3Q, 2Q or 1Q; 3Q to 2Q or 1Q; 2Q to 1Q
No change	Same quartile at both baseline and endpoint
- Shifts from quartile to quartile, both increases and decreases, will be summarized by treatment group in terms of frequency and percentage of the treatment group.

Questionable Height Measurements

- Questionable height measurements will be defined as either of the following:
 1. Any measurement obtained at a visit that is at least 0.05 cm less than the smallest measurement obtained at the previous visit; or
 2. Any measurement obtained at a visit that is at least 0.20 cm larger than the largest measurement obtained at the previous visit with the following caveat: if a subsequent visit was conducted and the mean of that visit is \geq the mean of the visit in question, then the measurement is acceptable; if a subsequent visit was not conducted then the measurement will be considered questionable. A hypothetical example appears below:

Visit	Height Measurement 1	Height Measurement 2	Height Measurement 3
6	100.0 cm	100.0 cm	101.0 cm
7	160.0 cm	101.0 cm	102.0 cm
8	101.0 cm	101.0 cm	101.0 cm

According to the rules outlined above, measurement 1 at Visit 7 (160.0 cm) would be flagged as questionable, as it is more than 0.20 cm larger than the largest measurement recorded at Visit 6 (101.0 cm). Additionally, because the mean of the subsequent Visit 8 measurements, 101.0 cm, is not greater than the mean of the Visit 7 measurements (121.0 cm) the measurement of 160.0 cm is still flagged as questionable.

Height Standard Deviation Scores (SDS)

 • Each participant's standard deviation score for each of the three required stadiometric height measurements is calculated as: [observed height measurement – standard median height for age at Visit 1] / [(standard 95th height percentile for age at the visit – standard 5th height percentile for age at the visit) / (2 x 1.645)]. • The standard median, 95th percentile, and 5th percentile values will be obtained from standard tables available on the website of the Centers for Disease Control and Prevention (CDC) [Guidance for Industry Orally Inhaled and Intranasal Corticosteroids: Evaluation of the Effects on Growth in Children, 2007]. • The standard deviation scores for each height stadiometric measurement at each visit will be calculated using the CDC percentiles and will then be averaged for each participant before being summarized by treatment group.

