Evidence derived from a Cochrane meta-analysis of randomised trials shows that regular use of ICS at low or medium daily doses is associated with a mean reduction of 0.48 cm per year in linear growth velocity and 0.61 cm in change from baseline in height during a one-year treatment in children with mild to moderate persistent asthma. The effect size of ICS on linear growth velocity appears to be associated more strongly with the ICS molecule than device or dose (low to medium dose range). The ICS-induced growth suppression seems to be maximal in the first year of therapy and less pronounced in the subsequent years of treatment [Zhang, 2014]. Another Cochrane review of the literature concluded that in persistent asthma, a small but statistically significant group difference in growth velocity was observed between low doses of ICS and low to medium doses of HFA-beclomethasone equivalent, favouring the use of low-dose ICS [Pruteanu, 2014]. In the four comparisons reporting linear growth over 12 months, a significant group difference was observed, clearly indicating lower growth velocity in the higher ICS dose group of 5.74 cm/y compared with 5.94 cm/y on lower-dose ICS (N = 728 school-aged children; mean difference (MD) 0.20 cm/y, 95% confidence interval (CI) 0.02 to 0.39). The authors concluded that in view of prevailing parents' and physicians' concerns about the growth suppressive effect of ICS, lack of or incomplete reporting of growth velocity in more than 86% (19/22) of eligible paediatric trials including those using beclomethasone and budesonide, is a matter of concern.

Therefore, there is good evidence to suggest that the first year of treatment with an inhaled corticosteroids is the most critical phase with respect to growth. In view of the seasonal variations in growth, one year is the minimum duration to reliably measure annual growth velocity [Tillmann, 2001].

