7.2. Secondary Growth Analyses

Secondary analyses pertinent to growth will be provided and are detailed. All secondary analyses described in the following sections will be based on the Growth Population, as defined in Section 4: Analysis Populations, unless otherwise specified.

7.2.1. Percentage of Participants with Growth Velocity Below the 3rd Percentile During the Double-Blind Treatment Period

The number and percentage of participants whose growth velocity during the double-blind treatment period is below the 3rd percentile will be summarized by treatment and listed. Details of the calculation of these percentiles can be found in Section 11.6.3. This characterization of growth velocity will be based on all available on- and off-treatment height data.

No formal statistical analysis is planned.

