11.7.2. Handling of Missing Data

Element	Reporting Detail
General	
 • Missing data occurs when any requested data is not provided, leading to blank fields on the collection instrument: 
 ○ These data will be indicated by the use of a “blank” in participant listing displays. Unless all data for a specific visit are missing in which case the data is excluded from the table. ○ Answers such as “Not applicable” and “Not evaluable” are not considered to be missing data and should be displayed as such.
Growth Analyses	
Missing height data for the primary and supportive analyses of growth velocity described in Section 7: Growth Analyses, will not be imputed and will be treated as missing (assuming MAR).
 
For the supportive analysis defined in Section 7.1.6, two approaches have been defined to assess the effect of missing data. For these analyses, the population of interest will be the Intent-to-Treat (ITT) population, as defined in Section 4: Analysis Populations.
 
The final Week 52 (Visit 18) height measurement is scheduled for day 365 with a visit window of -5/+2 days. In cases where the final height measurement at week 52 is missing, (i.e. there is not a scheduled or unscheduled height measurement available for any of days 360 to 367 inclusive) the missing height measurement will be imputed at day 365 using Multiple Imputation based on two different approaches:
 
Approach 1: Use the ‘worst growth rate’ (i.e., smallest growth velocity) from participants from the FF 50 treatment group who complete the double-blind treatment period as the central value for imputations of missing data in the FF treatment group, and the ‘worst growth rate’ from participants from the placebo group who complete the double-blind treatment period as the central value for imputations of missing data in the placebo treatment group (Supportive Estimand IX).
 
Implementation of Approach 1: The steps are the same in both treatment arms, so the method for one arm will be described below:
 
Let y_{it} be the value of the height measurement of participant i at day $t = 0, \dots, 365$. Assume there are n participants in this treatment arm and of those: n_{obs} have a week

Element	Reporting Detail

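### The below-3rd-percentile count sets a period-average growth velocity against the standard for the child's age at the end of the period, about 26 weeks later for completers; the look-up age should match the interval

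*SAP*

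**What the plan says.** SAP 11.6.3 builds the velocity from "Stadiometric height measurements obtained at Baseline (Visit 5) and during the double-blind treatment period (Visit 6 up to and including Visit 18"), and adds: "The slope of this regression line will be the participant’s growth velocity for that study period". SAP 11.7.2 fixes the end of the interval: "The final Week 52 (Visit 18) height measurement is scheduled for day 365 with a visit window of -5/+2 days".

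For the 3rd-percentile count, the same section takes cut-offs from a published British table. The child's velocity is "programmatically compared to these imported data using the 3rd percentile value of the age closest to the" child's own age. The age meant is not the one at mid-interval but the one on the closing date, which is Visit 18 for a child who reaches it and the Early Withdrawal Visit otherwise. On- and off-treatment heights both count. SAP 7.2.1 gives the output: "The number and percentage of participants whose growth velocity during the double-blind treatment period is below the 3rd percentile will be summarized". The summary is split by arm, the children concerned appear in a listing, and no formal analysis is foreseen.

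The quartile look-ups in SAP 11.6.3 follow the same pattern. Baseline velocity (Visits 1, 3 and 5) is read at the age at Visit 5. Endpoint velocity (Visits 12 to 18) is read at the age at the last visit included.

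The documents do not reproduce the percentile values, give the table's age spacing, or say whether its velocities refer to the middle or the end of an interval. SAP 11.6.2 defines age in whole years, and only at Visit 1. The precision of age at Visit 18 is not stated.

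**The concern.** A slope fitted over a year describes growth around the middle of that year, yet the rule picks the standard for a child half a year older. If the low-growth threshold changes with age, the two sides of the comparison do not refer to the same age. A falling threshold would make the cut-off too lenient, and some slow growers would not be flagged.

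The mismatch also depends on follow-up: a child whose heights stop early has a smaller offset. The baseline and endpoint quartile look-ups carry different offsets as well, so a quartile shift can partly reflect the look-up.

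This is the first-listed secondary growth endpoint in a growth-safety trial. It is the one tied to an absolute low threshold, and expected counts are small, so a few children matter to how the table reads.

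**Working it through.** **Plan's own figure.** The documents give no figure for this endpoint. Their one design figure is reproduced: with SD 1.2 cm/yr and 203 per arm (Protocol 9.2.1), the 95% half-width is 1.96 × 1.2 × √(2/203) = 0.2335. The width is 0.467 cm/yr, within the stated limit of 0.5.

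**Time the slope represents.** The height visits fall at Weeks 0, 4, 8, 12, 16, 28, 40 and 52 (Protocol 7.1). When velocity changes smoothly (a quadratic height curve), a least-squares slope equals the velocity at t* = mean + S3/(2 × S2), where S2 and S3 are the sums of squared and cubed deviations from the mean week.

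- Mean = 160/8 = 20; S2 = 2368; S3 = 26880.
- t* = 20 + 26880/4736 = Week 25.7.
- Offset at Week 52: 52 − 25.7 = 26.3 weeks. Using the plain midpoint, it is 26.0 weeks.

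**Offsets elsewhere** (half the interval, age taken at the last visit in it).

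| Look-up | Offset after midpoint |
|---|---|
| Last height at Visit 8 / 9 / 12 / 15 | 6 / 8 / 14 / 20 weeks |
| Last height at Visit 18 | 26 weeks |
| Baseline quartile (Visits 1–5, days −112 to 1) | 113/2/7 = 8.1 weeks |
| Endpoint quartile (Visits 12–18, days 197 to 365) | 168/2/7 = 12 weeks |

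**Effect on the count.** The assumed quantity is g, the yearly fall in the 3rd-percentile velocity. The cut-off is then 0.5 × g too low. Take a group in which 3% truly lie below the matched cut-off, with SD 1.2. The counted proportion is Φ(−1.881 − 0.5g/1.2). For a group growing 0.48 cm/yr slower (the meta-analysis figure in Protocol 2.1, used for scale only), add 0.48/1.2 inside the bracket.

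| g (assumed) | Group truly at 3% (6.1 of 203) | Slower group, truly 6.9% (14.1 of 203) | Difference, points | Ratio |
|---|---|---|---|---|
| −0.1 (rises) | 3.3% (6.7) | 7.5% (15.2) | 4.2 | 2.28 |
| 0 (flat) | 3.0% (6.1) | 6.9% (14.1) | 3.9 | 2.31 |
| 0.1 | 2.7% (5.5) | 6.4% (13.0) | 3.7 | 2.34 |
| 0.2 | 2.5% (5.0) | 5.9% (12.0) | 3.4 | 2.38 |
| 0.3 | 2.2% (4.6) | 5.4% (11.0) | 3.2 | 2.41 |

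With g from 0.1 to 0.3, the group at 3% is counted as 2.7% to 2.1% at SD 1.0, and as 2.8% to 2.5% at SD 1.7.

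**Part-year slopes.** The Growth Population (SAP 4) admits a child with heights only to Week 12: Visits 6, 7 and 8 are on treatment and the first and third are 8 weeks apart, against the required 7. For Weeks 0, 4, 8 and 12, S2 = 80. The slope's measurement error is therefore √(2368/80) = 5.4 times that of a full year, whatever the height error is. Protocol 2.2 itself says that "one year is the minimum duration to reliably measure annual growth velocity".

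**The case against.** The strongest objection is that the direction is unproven. A reader might infer that the rule demonstrably under-counts slow growers, but the documents do not support that. The cut-offs sit in an external table. Without its values and its indexing, nobody can say from the protocol and SAP that the threshold falls with age at Visit 18 (about 6.3 to 10.3 years for boys and 6.3 to 9.3 for girls, adding 68 weeks to the entry ages), or that the end-of-period age is the wrong one to use. This stands, and it makes the under-count conditional.

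Nor can one say that every completer's cut-off is too low. Nearest-age matching moves some children to a younger tabulated age. If age at Visit 18 were in completed years, as at Visit 1, it would be understated by about half a year on average and would roughly cancel the offset. That also stands, but a cancellation that depends on an undefined age precision and varies child by child is not a safeguard.

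It would also be wrong to call this the only endpoint that picks out individual slow growers: children whose quartile decreases are listed too (SAP 7.2.2).

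The rule is identical in both arms, the endpoint is descriptive, and the absolute effect is small. All three are correct and limit the weight of the point.

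On part-year slopes, children who stop treatment are followed with emphasis on the 52-week height (Protocol 5.5.1), so a child with data only to Week 12 is near the extreme. The added noise tends to raise a count in the lower tail, against the direction of a lenient cut-off. The net effect, and any imbalance between arms, cannot be signed from the documents.

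**Conclusion.** The mismatch is real: a period-average velocity is paired with an end-of-period age. The gap is about 26 weeks for completers and 6 to 20 weeks when the last height is at Visits 8 to 15, with different gaps again for the two quartile look-ups. The endpoint-quartile figure uses the visits in SAP 11.6.3; SAP 7.2.2 describes that endpoint as the last 12 weeks, which would halve the offset to 6 weeks.

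An under-count follows only if the 3rd-percentile velocity falls with age in this range and the table gives velocity at the stated age. Under an assumed fall of 0.1 to 0.3 cm/yr per year of age, about 0.5 to 1.5 of 203 children are missed in a group truly at 3%, and about 1 to 3 of 203 in a group growing 0.48 cm/yr slower. The effect is zero if the cut-off is flat and reverses if it rises. The risk difference shrinks slightly, the ratio barely changes, and the primary ANCOVA and sample size are unaffected.

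It is worth correcting because the rule is explicit, the expected counts are small, and the change costs almost nothing.

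**What to change.** In SAP 11.6.3:

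1. Look up the 3rd percentile and the quartile cut-offs at the child's decimal age at the midpoint of the interval over which the slope was fitted, interpolating between tabulated ages.
2. Before unblinding, confirm how each cited table is indexed. If it is not velocity at the stated age, use the matching point and say so.
3. State the precision of age. SAP 11.6.2 already imputes day 15 to the birth month and year, so decimal age can be derived.
4. Keep every child in the main percentage, and add a supplementary row for children with a Week 52 height.

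The main percentage should not be restricted to children with a Week 52 height. That would condition on a post-randomisation outcome, depart from the plan's use of all available heights, and could drop slow growers who withdraw early.

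The cost is a few lines of SAP text, a changed look-up program and one extra table row. No new data are needed.

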4. ANALYSIS POPULATIONS

Population	Definition / Criteria	Analyses Evaluated
Total	
 Comprised of all participants screened and for whom a record exists on the study database. 	
 Study Population Safety
Intent-to-Treat (ITT)	
 Comprised of all randomised participants who receive at least one dose of study treatment. This population will be based on the treatment to which the participant was randomised. Any participant who receives a treatment randomisation number will be considered to have been randomised. 	
 Study Population Safety (including Growth Analyses) Efficacy
Growth	
 Comprised of all ITT participants who have stadiometric height assessments from at least three post-randomisation, on-treatment clinic visits (i.e., including all available height measurements after Visit 5 up to and including Visit 18, without exclusion) during the double-blind treatment period. Note: To be included in the Growth population, the 1st and 3rd height measurements need to be at least 7 weeks apart. 	
 Study Population Safety (i.e., Growth Analyses)

Refer to [Appendix 9](#): List of Data Displays which details the population used for each display.

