7. GROWTH ANALYSES

7.1. Primary Growth Analyses

7.1.1. Endpoint / Variable

The primary endpoint is the growth velocity (cm/yr) over the double-blind treatment period, as determined by stadiometry. Details regarding the calculation of growth velocity are provided in Section 11.6.3.

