7.1.6. Supportive Analyses

Details of the planned displays are provided in [Appendix 9: List of Data Displays](#) and will be based on GSK data standards and statistical principles.

For each of the following analyses, the estimate of the mean treatment difference in growth velocity during the double-blind treatment period will be provided, using all the available height data provided while participants were on randomised double-blind treatment, unless otherwise specified. By-treatment summaries of growth velocity over the baseline, treatment, and follow-up periods will also be provided. The change from baseline will also be summarised by treatment group.

Supportive Estimand I for Primary Endpoint
	

 • Given that participants who prematurely discontinue randomised treatment may be administered other medications that may affect growth, a supportive estimand (Supportive Estimand I) will be defined for the primary endpoint, as defined in Section 7.1.1. • This estimand will be based on the Growth Population, as defined in Section 4: Analysis Populations. • The summary measure will be as described in Section 7.1.2 for the primary analysis, and the statistical analyses/methods (i.e., model specification, model checking and diagnostics, and model results presentation) will be as described in Section 7.1.5 for the primary analysis. • The strategies for handling the intercurrent events/events leading to missing data for this estimand will be as described in Section 7.1.4, apart from the intercurrent event of “Discontinuation of Randomised Treatment” which will be handled as described below: 	

Event
	
Handling Strategy

Discontinuation of Randomised Treatment
	
Only available height data while the participant is on randomised double-blind treatment will be used in the analysis.

Supportive Estimand II for Primary Endpoint	

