
 Another supportive estimand defined for the primary endpoint (as defined in Section 7.1.1) will be Supportive Estimand II. This estimand will be based on the Growth Population (as defined in Section 4: Analysis Populations) and will exclude participants who presented Tanner Stage ≥ 2 at any time during the double-blind treatment period or follow up period. The summary measure will be as described in Section 7.1.2 for the primary analysis, and the statistical analyses/methods (i.e., model specification, model checking and diagnostics, and model results presentation) will be as described in Section 7.1.5 for the primary analysis. The strategies for handling the intercurrent events/events leading to missing data for this estimand will be as described in Section 7.1.4, apart from the intercurrent event of “Discontinuation of Randomised Treatment” which will be handled as described below: 	
Event	Handling Strategy
Discontinuation of Randomised Treatment	Only available height data while the participant is on randomised double-blind treatment will be used in the analysis.
Supportive Estimand III for Primary Endpoint	

 Another supportive estimand defined for the primary endpoint (as defined in Section 7.1.1 but excluding questionable height data as defined in Section 11.6.3) will be Supportive Estimand III. This estimand will be based on the Growth Population (as defined in Section 4: Analysis Populations) The summary measure will be as described in Section 7.1.2 for the primary analysis, and the statistical analyses/methods (i.e., model specification, model checking and diagnostics, and model results presentation) will be as described in Section 7.1.5 for the primary analysis. The strategies for handling the intercurrent events/events leading to missing data for this estimand will be as described in Section 7.1.4 for the primary analysis, apart from the intercurrent event of “Discontinuation of Randomised Treatment” which will be handled as described below: 	
Event	Handling Strategy
Discontinuation of Randomised Treatment	Only available height data while the participant is on randomised double-blind treatment will be used in the analysis.
Supportive Estimand IV for Primary Endpoint	

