11.9.10. Non-ICH Listings

Non-ICH: Listings					
No.	Population	GSK Standard / Example Shell	Title	Programming Notes	Deliverable [Priority]
Study Population					
23.	ITT	Non-Standard POP_L2	Listing of Study Treatment Misallocations		SAC
24.	ITT	Non-Standard POP_L3	Listing of Height Assessed by Stadiometry	Include all visits, including early withdrawal from study and treatment discontinuation visits.	SAC
25.	ITT	Non-Standard POP_L4	Listing of Asthma History at Screening		SAC
26.	ITT	MH2	Listing of Medical Conditions	Includes both current and past medical conditions.	SAC
27.	Growth	Non-Standard POP_L5	Listing of Subjects Presenting Tanner Stage 2 or Higher		SAC
28.	ITT	CM6	Relationship between ATC Level 1, Ingredient and Verbatim Text for Non-Respiratory Medications		SAC

Non-ICH: Listings					
No.	Population	GSK Standard / Example Shell	Title	Programming Notes	Deliverable [Priority]
Safety (Growth)					
29.	Growth	GRO_L1	Listing of Growth Velocity (cm/yr)	Include flags for: 
 ○ Subjects presenting Tanner Stage ≥ 2 ○ Subjects with Questionable Height Measurements ○ Subjects with height measurements taken after receiving rescue systemic corticosteroids Subjects with height measurements taken after receiving rescue inhaled and/or intranasal On-treatment and on-and off-treatment growth velocity will be displayed separately.	SAC
30.	Growth	Non-Standard GRO_L1	Listing of Subjects Below the 3 rd Percentile of Growth Velocity During the Double-Blind Treatment Period	Using all the available on-and-off-treatment height data.	SAC
31.	Growth	Non-Standard GRO_L1	Listing of Subjects with Decrease from Baseline to Endpoint in Growth Velocity Quartile	Using all the available on-and-off-treatment height data.	SAC
Safety (AEs)					
32.	ITT	Non-Standard SAF_L1	Listing of Asthma Exacerbations		SAC
33.	ITT	SAF_L3	Listing of Study Treatment Inhaler Malfunctions	If any events reported.	SAC

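### The questionable-height rule deletes ordinary growth at a child's last height visit in Supportive Estimands III and VI; the effect on the treatment difference is small, and the direction of bias in early leavers depends on a step the SAP does not state

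*SAP*

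**What the plan says.** SAP Section 11.6.3 defines two kinds of questionable height. Rule 1 catches a reading 0.05 cm or more below the previous visit's smallest reading. Rule 2 catches a reading that "is at least 0.20 cm larger than the largest measurement obtained at the previous visit". Rule 2 has one release: the reading stands if a later visit took place and its mean is no lower than the mean of the visit under test. With no later visit there is no release: "if a subsequent visit was not conducted then the measurement will be considered questionable". The 0.20 cm does not vary with the gap between visits. Under the Time and Events Table (Protocol 7.1), height is measured at Weeks -16, -8, 0, 4, 8, 12, 16, 28, 40 and 52 and 8 weeks after treatment, so the gaps are 4, 8 or 12 weeks.

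Supportive Estimands III and VI (SAP 7.1.6) apply the filter. Estimand III takes the primary endpoint "as defined in Section 7.1.1 but excluding questionable height data as defined in Section 11.6.3". SAP 7.1.1 defines that endpoint: "The primary endpoint is the growth velocity (cm/yr) over the double-blind treatment period, as determined by stadiometry". Table 1 in SAP 2.1 explains that single height measurements are removed, not children. SAP 11.6.3 also makes the average of the triplicate the child's height at that visit. It does not say how that height is formed once one or two of the three readings are removed.

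The default in SAP 11.6.3 is: "Stadiometry measurements obtained during the Early Withdrawal/Early Treatment Discontinuation Visit will be included in the calculation of the growth velocity". Growth Population membership (SAP 4) needs three on-treatment height visits: "To be included in the Growth population, the 1st and 3rd height measurements need to be at least 7 weeks apart". Week 12 (after Visits 6, 7 and 8) is therefore the earliest scheduled last height. SAP 7.1.6 adds "By-treatment summaries of growth velocity over the baseline, treatment, and follow-up periods will also be provided", and Listing 29 (SAP 11.9.10) carries a flag for "Subjects with Questionable Height Measurements".

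**The concern.** A child measured on schedule is expected to exceed the rule 2 limit at every visit. At earlier visits the next height usually clears the reading. At the last height visit nothing can, so the clause treats normal growth as suspected error. If single readings are deleted, those that show normal growth go and the low ones stay. That is selection on the outcome as well as loss of data.

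Estimands III and VI are meant to show that the result is robust to measurement error. A filter that removes valid last heights cannot do that cleanly for children who leave early. The rule also names no study period, and does not say whether Visit 20 or an off-treatment height may clear an earlier reading. Two programmers could therefore produce different tables and different flags from the same data.

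**Working it through.** **The SAP's own example.** Visit 7 readings are 160.0, 101.0 and 102.0 cm, with mean 363.0/3 = 121.0 cm, as stated. The 160.0 cm reading exceeds the Visit 6 maximum of 101.0 cm, and the Visit 8 mean of 101.0 cm does not clear it, so the flag reproduces. Read literally, the rule also flags 102.0 cm (1.0 cm above 101.0, not cleared), which the example does not mention.

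**Ordinary growth against the limit.** Protocol 2.2 quotes 5.74 and 5.94 cm/yr. Growth = velocity × days/365.25.

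- 4 weeks (28 days): 0.44 to 0.46 cm
- 8 weeks (56 days): 0.88 to 0.91 cm
- 12 weeks (84 days): 1.32 to 1.37 cm
- Time to grow 0.20 cm: 0.20/5.94 × 365.25 = 12.3 days; 0.20/5.74 × 365.25 = 12.7 days

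Expected growth exceeds 0.20 cm at every scheduled gap. This step needs no assumption.

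**Size of the bias, by simulation.** Inputs from the documents are the visit schedule, triplicates recorded to 0.1 cm (Protocol 7.3.1), mean velocity 5.74 or 5.94 cm/yr and between-child SD 1.2 cm/yr (Protocol 9.2.1). The documents give no measurement-error SD, so it is assumed: reading/visit SD pairs from 0.05/0.05 to 0.3/0.3 cm. Rules 1 and 2 are applied to each reading and a least-squares slope is fitted. Bias is the filtered minus the unfiltered mean slope over the same visits, with 60,000 to 120,000 children per setting.

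With surviving readings re-averaged:

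- Last height at Week 12: all three readings flagged in 39-95% of children; velocity 0.03-0.54 cm/yr too low (under 0.01 at 0.03/0.03 cm).
- Last height at Week 16: 0.02-0.31 cm/yr too low.
- Last height at Weeks 28-52: visit wholly flagged in 87-100%; bias -0.02 to +0.28 cm/yr.

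With the whole visit dropped when a reading is flagged: about -0.04 to +0.5 cm/yr at Week 12 and -0.03 to +0.4 at Week 16, near zero at low error and upward at high error.

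With an Early Withdrawal height after the last scheduled one and re-averaging: -0.19 to -0.01 cm/yr when it falls 1-27 days after Week 12, and -0.10 to +0.08 when it falls 1-83 days after Week 16.

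**Treatment difference in III/VI.** The planned half-width is 1.96 × 1.2 × √(2/203) = 0.233 cm/yr, consistent with the protocol's full width of at most 0.5. Arm means are set at 5.94 and 5.94 - 0.48 = 5.46 cm/yr, a linear effect. With 0-10% leavers in each arm, the difference shifts by at most 0.005 cm/yr if Visit 20 may clear Visit 18, and by at most 0.022 if it may not. If 10% of one arm only have a last height at Week 12-16, the shift is 0.003-0.045. A rough check on that upper end: 0.10 × (0.54 + 0.31)/2 = 0.043.

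**Alternatives for the last-visit clause.** Bias (cm/yr) for a last height at Week 12, mean 5.94, re-averaging. The scaled limit uses an assumed ceiling of 5.94 + 1.88 × 1.2 = 8.2 cm/yr.

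| Reading/visit SD (cm) | As written | Last visit exempt | Interval-scaled |
|---|---|---|---|
| 0.1/0.1 | -0.25 | +0.01 | 0.00 |
| 0.2/0.2 | -0.50 | +0.23 | +0.08 |
| 0.1/0.3 | -0.15 | +0.54 | +0.16 |
| 0.3/0.3 | -0.54 | +0.58 | +0.18 |

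**The case against.** The best defence is that little depends on this. The primary analysis never uses the filter, no hypothesis is tested, and the III/VI difference hardly moves. That stands, and it sets the severity. The size in early leavers also rests on assumed error. Protocol 7.3.1 asks for trained staff, calibration, a consistent time of day and reproducible triplicates. A reading SD of 0.3 cm implies an expected triplicate range of about 0.51 cm, so the top of the range is pessimistic.

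A reader might infer several stronger points that the documents do not support.

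- *Velocity in early leavers is always biased low.* This follows only if surviving readings are re-averaged. Table 1 of the SAP points that way, but Section 11.6.3 leaves dropping the visit open, and the sign can then reverse.
- *Up to 10% of children are affected.* The 10% in Protocol 9.2.1 is withdrawal from study medication within 12 weeks. Protocol 5.5.1 asks those children to keep attending, and schedules an Early Withdrawal visit for those who leave the study. A later height can clear the earlier one.
- *The filter contradicts the Growth Population minimum or the rule that Early Withdrawal heights are used.* SAP 4 counts height visits before any exclusion, and Estimand III is an explicit exception to the default calculation. A child left with Weeks 0, 4 and 8 still has a slope.
- *Follow-up velocity is destroyed and Listing 29 flags nearly every completer.* If the rule reached Visit 20, follow-up velocity would be computable in only 0-30% of children, and 99-100% of completers would carry the flag, against 0-73% if only Visits 1-18 could raise it. But 7.1.1 and Estimand III tie the exclusion to the double-blind endpoint. The gap is unstated scope, and the flag changes no estimate.

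**Conclusion.** The clause is wrong as written: it removes ordinary growth at a child's last height visit from Estimands III and VI. That conclusion rests only on the SAP's rule, the visit schedule and the protocol's own velocities. The size and sign of the resulting bias in children last measured at Week 12-16 are conditional on the measurement error, which the documents do not give, on how a visit height is re-formed after deletion, and on whether an Early Withdrawal height follows. Removal of single readings with re-averaging is the closest reading of SAP Table 1, and on that reading the bias is downward. The effect on the between-arm comparison is well inside the planned precision. This is a minor defect in two supportive analyses, worth correcting because correction is cheap.

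**What to change.** Before unblinding, amend SAP Section 11.6.3.

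1. Replace the no-later-visit clause. At a last height visit, flag a reading only if it exceeds the previous visit's largest reading by more than the 97th-percentile velocity for age and sex × elapsed time, plus 0.20 cm. The velocity charts of randomisation criterion 1c (Protocol 5.4) can supply the percentile. Do not simply exempt last visits: at larger error that biases leavers upward, by as much as +0.59 cm/yr at Week 12 and +0.37 at Week 16.
2. State whether a visit height is re-averaged from the unflagged readings or the whole visit is dropped.
3. State that only visits with stadiometry count as previous or subsequent; that any later height, off-treatment or at Visit 20, may clear an earlier one; and that the filter and the Listing 29 flag apply to treatment-period heights only.

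Items 2 and 3 are clarifications that accompany item 1. The cost is SAP wording and programming, with no new data.

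The scaled limit is not free of bias. Rule 1 still deletes falls, so some upward bias remains at larger error: 0 to +0.21 cm/yr at Week 12 and 0 to +0.14 at Week 16 with the assumed 8.2 cm/yr ceiling (-0.04 to +0.21 and -0.02 to +0.14 over ceilings of 7.5-9.0). At 0.1/0.3 cm it is as large as the present bias, with the opposite sign. An annual percentile scaled to a few weeks will also flag a few fast or seasonal growers wrongly. The chart values are not in the documents, so the chosen limit should be checked against them.
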